### **Data and Safety Monitoring Plan (DSMP)**

Although no high risk procedures are being conducted as part of this study, we will be following patients on an FDA approved study medication for 8 weeks. For this reason, we have elected to utilize the Data Safety Monitoring Board of the Department of Psychiatry and Behavioral Sciences as a third-party oversight committee. The DSMB is described in detail below. In addition, study clinicians will be available by pager 24 hrs/7 days a week during the period between screening and study completion. Should a subject experience a study related emergency or should active suicidal ideation develop, either [name] or [name] will be immediately notified. Drs. [name] and [name] are board certified psychiatrists with extensive experience in the treatment of psychiatric emergencies. If the assessment in question was done by a clinician other than either of them, one of them will immediately contact the subject and will evaluate the need for further medical or psychiatric treatment and will arrange medical or psychiatric follow-up if indicated. They will evaluate each case individually to make a determination regarding whether the subject can remain in the study or whether the subject should be terminated in addition to receiving a mental health referral.

#### **Adverse Event Reporting**

Enrolled participants will be monitored closely by study clinicians for any adverse events. All adverse events will be collected using the NCI Common Terminology Criteria for Adverse Events version 4.0. If any overt study-related adverse events occur, a decision will be made about study continuation. Additionally, a record of adverse events for study participants will be reported to the DSMC on a regular basis. Subjects will be closely monitored during the course of the study for development of any serious or unexpected adverse reactions. Those events meeting Emory IRB criteria for a reportable event will be reported to the IRB or the Winship Cancer Institute DSMC according to standard regulations and procedures. The Emory IRB Reportable Events Guidelines are included in an attachment.

#### **Stopping rules**

Individuals who exhibit significant suicidal ideation as indicated above will be discontinued from the study. Individuals who exhibit any evidence of an allergic reaction including rash, hives or difficulty breathing and individuals who exhibit more than a two-fold elevation in liver transaminases will be discontinued from the study and followed until the allergic reaction

resolves or the transaminases return to baseline. Individuals who exhibit suicidal ideation or a serious adverse reaction to riluzole will be unblinded by the study pharmacist, and clinical management will be supervised by an unblinded study physician. Patients who have taken less than 75% of their medication may be excluded from study participation. If study removal occurs at or after the 4 week study visit, the patient will undergo exit safety laboratory testing and physical examination. Urine drug tests will be conducted at each visit (except week 2) using test kits. Individuals who test positive for drugs of abuse may be terminated at the discretion of the PI.

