### **Description of Study Procedures (Baseline 1, Startle Study, Baseline 2 and Weeks 1-8)**

All eligible participants with a CRP>3mg/L and a Fatigue Score  $\geq 4$  will complete Baseline 1, be randomized to receive riluzole (100 mg/d) or placebo at Baseline 2, and proceed to study visits at Weeks 1, 2, 4, and 8.

During the Baseline 1 visit and on Week 1 and Week 8, subjects will undergo magnetic resonance spectroscopy (MRS). Between baseline 1 visit and baseline 2 visit, participants will have the option of undergoing a parallel Startle Test Study protocol. This protocol will consist of either 1 or 2 visits, for completing psychiatric assessments and self-report forms and for completing a psychophysiological startle task. A schedule of all assessments is provided in Table 1. Approximately 30 mL of blood will be drawn at the same time of day between 8-10AM (to reduce potential circadian effects) under sterile conditions at Baseline 1 and 2 and Weeks 1, 4 and 8. Screening/safety labs are not time dependent. Safety labs will be completed at Baseline 2, Week 4 and Week 8. At each visit, self-report forms with urine toxicology will occur as well as recording of concomitant medications and adverse events. Neurocognitive testing will be completed on Baseline 1, Baseline 2 and Week 8. Where indicated, participants will be administered the neurocognitive tests and the scanning sequence of the MRS will be completed based on scanner availability and at the discretion of the PI or PI's designee. Subject will be read MRI instructions 48hrs prior to Baseline 1, Week 1, and Week 8 visits to have the subject avoid specific foods, medications, alcohol and cigarettes starting 24hrs prior to the MRS scan. A light lunch/snack may be provided after the fasting lab work.

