**+ - for patients with a CRP>3mg/L and a Single Item Screening Scale for Fatigue Score ≥4**

**\* - for patients completing the main branch of the Riluzole Study**

**\*\* - for patients who opt for to complete the Startle Test Study**

**Key:**

**Main Riluzole Study**

\*Screening/ Safety Labs: CBC w/Diff, Metabolic Panel, hCG quantitative serum, TSH, Urinalysis w/micro at Screening and Week 8 only, Urine drug test all visits (test kit), except week 2 visit; Testing for CRP, Hepatitis B and C and HIV will be conducted on the screening visit only, unless otherwise approved by the PI. A Rapid C Reactive Protein finger prick may also be obtained by trained research staff using a rapid CRP finger prick test at the discretion of the investigator to expedite determining eligibility for research participation.

\*Psychiatric Assessments: WRAT-3, MMSE, CTQ, QID-S, Single Item Screening Scale for Fatigue

\*Research Blood: Cytokine Multiplex, TRP, KYN, mRNA analysis, methylation analysis, and gene analysis (collected under fasting conditions)

\*Self-Report Forms: IDS-SR, MFI, PROMIS-Fatigue, BAI, PSQI, Assessment of Pain level, PHQ-9, Single Item Screening Scale for Fatigue, Baycrest Memory Scale

\*Neurocognitive Tests:

Baseline 1 - EEfRT, Finger Tapping Task (FTT), The Trail Making Test (TMT), Digit Symbol Task, Reaction Time Task (CANTAB)

Baseline 2 - Rey Auditory Verbal Learning Test (RAVLT), Delayed Matching To Sample (CANTAB), Spatial Working Memory (CANTAB), Stroop Color and Word Test

Week 8- EEfRT, Finger Tapping Task (FTT), The Trail Making Test (TMT), Digit Symbol Task, Reaction Time Task (CANTAB), Rey Auditory Verbal Learning Test (RAVLT), Delayed Matching To Sample (CANTAB), Spatial Working Memory (CANTAB), Stroop Color and Word Test

[figure not shown]

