### **Compliance**

Patients will be asked to fill out a medication log and bring in their pill bottles at each study visit. Patients who have taken less than 75% of their medication may be excluded from study participation. If study removal occurs at or after the Week 4 study visit, the patient will undergo exit safety laboratory testing and physical examination.

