## 12. Potential Study Risks:

**Main Riluzole Study Risks:** There are 4 major areas of potential risk in the proposed study stemming from 1) neuropsychiatric assessments, 2) blood drawing, 3) MRS scanning and 4) riluzole treatment. Neuropsychiatric assessments may uncover unpleasant feelings about the subject's present emotional state. The risks of blood drawing include discomfort, bruising, infection, bleeding and fainting. Undergoing MRS scan poses no more risk than undergoing a routine MRI scan. Nevertheless, physical discomfort due to lying in the scanner, occasional headaches due to scanner sounds and previously unrecognized claustrophobic attacks are the

prominent adverse effects of the procedure. Major complications of riluzole (Rilutek) include an allergic reaction to riluzole or the components of the tablet and hepatic toxicity. Riluzole is contraindicated in individuals who have a history of hypersensitivity reactions to riluzole or any of the tablet components and in individuals who have hepatic disease or who have baseline transaminases greater than 3 times the upper limit of normal. The drug is also contraindicated in women who are pregnant. Subjects of childbearing ability must agree, with the study doctor or PI's designee, on a method of birth control to use throughout the study. To ensure no contraindications with alcohol, participants will be told not to consume more than 1 alcoholic drink per day while on study medication (12 fl oz of beer, 5 fl oz of wine, 1.5 fl oz shot of distilled spirit, and also not to consume any alcohol within 24 hours of a study visit brain scan. Of the most commonly observed adverse events associated with the use of RILUTEK in 1,396 individuals with amyotrophic lateral sclerosis, those reported more frequently than with placebo treatment were: asthenia, nausea, elevations in liver function tests, dizziness, decreased lung function, diarrhea, abdominal pain, pneumonia, vomiting, vertigo, circumoral paresthesia, anorexia and somnolence. Table 2 shows the most common treatment-emergent adverse reactions considered possibly related to medication and for which the incidence was  $\geq 1\%$  in an open label Phase IV confirmatory trial for amyotrophic lateral sclerosis of 414 patients.

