**Adequacy of Protection Against Risks**

Protection Against Risk:

Every effort will be taken to prevent injury or distress that may result from this study. Care will be taken to avoid bringing about undue psychological distress during the self-reported questionnaires. In the event that a subject becomes unduly distressed or scores  $>32$  on the IDS-SR (indicating moderate to severe depressive symptoms) or endorses a score  $>2$  on the suicide item of the IDS-SR (Question 18) or a score  $\geq 3$  on the PHQ-9 suicide item, the PI or his designee will be immediately contacted, and an appropriate clinical intervention plan will be developed. Emory has inpatient, outpatient and emergency room psychiatric services at all recruitment and evaluation sites. In addition, the PI [name] is a Board-certified psychiatrist and has extensive experience in administering standardized clinical assessments and handling psychiatric emergencies. As for blood drawing, standard sterile procedure for blood withdrawal will be used. Blood draws will be conducted by trained phlebotomists with

significant experience in the technique. In addition, the volume of blood withdrawn for this study will not exceed 40 mL over the course of the study (including screening and assessment visits). To minimize discomfort during the MRS scanning, patients will be provided with a head cushion and earplugs. Patients will also be informed about the progress of the procedure through a remote microphone. In the case of patients developing acute anxiety or panic, the scanning session will be terminated and patient provided enough support to cope with the feelings induced by the scanner. If a patient is uncomfortable with the skin cleansing during the psychophysiological task, it will be omitted. Patients will be told about the airblast prior to beginning the task. If they are uncomfortable with this or any part of the task, the task will be stopped. To reduce the likelihood of adverse reactions to riluzole, all patients will have a thorough history of allergic reactions reviewed and their first dose of riluzole will be administered under supervision of a study physician or nurse practitioner. In addition, all patients will be screened for evidence of liver disease including a screen for liver transaminases as well as hepatitis B and C and HIV. Liver transaminases will also be monitored at weeks 4 and 8, and subjects will be instructed to inform staff of any gastrointestinal symptoms.

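### A woman who takes study drug and leaves before Week 4 has no required liver test, on drug or at exit, because the exit-safety rule starts only at Week 4

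*Combined protocol and SAP*

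**What the plan says.** Study drug starts at the Baseline 2 visit, with later visits at Weeks 1, 2, 4 and 8 (Section 6, Description of Study Procedures, and Table 1). The same section sets the laboratory schedule: "Safety labs will be completed at Baseline 2, Week 4 and Week 8". Section 12, Adequacy of Protection Against Risks, repeats it for the liver: "Liver transaminases will also be monitored at weeks 4 and 8, and subjects will be instructed to inform staff of any gastrointestinal symptoms".

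Blood is also drawn at Week 1, but as research blood, which the key to Table 1 lists as "Cytokine Multiplex, TRP, KYN, mRNA analysis, methylation analysis, and gene analysis". Table 1 shows no blood draw at Week 2, and it places the physical examination at screening and Week 8 only.

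One rule, given in two places, covers what is done when a woman leaves. Section 12, Stopping rules, reads: "If study removal occurs at or after the 4 week study visit, the patient will undergo exit safety laboratory testing and physical examination". Section 6, Compliance, sets the same condition: "If study removal occurs at or after the Week 4 study visit". The Stopping rules also provide that "individuals who exhibit more than a two-fold elevation in liver transaminases will be discontinued from the study", with follow-up until the values are back at baseline. Section 12, Potential Study Risks, shows why the liver is watched: "Major complications of riluzole (Rilutek) include an allergic reaction to riluzole or the components of the tablet and hepatic toxicity".

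**The concern.** The exit rule takes effect at the same visit as the first scheduled on-drug liver test. The two arrangements therefore leave the same women uncovered: those who have taken study drug and leave before that visit.

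The transaminase stopping rule is triggered by a laboratory value. It has no time limit, so it can act before Week 4, but only if someone has taken a sample. In a woman who leaves at Week 1 or 2, nothing in the plan requires that sample. Gastrointestinal complaints are a plausible reason to stop early (Table 2 lists nausea at 6% and stomach discomfort at 3%), and she could stop for one of these without her transaminases ever being checked.

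At stake is the detection and follow-up of a rise without symptoms, which the protocol itself wants followed. The DSMB would learn of the dropout, its reason and any recorded safety concern, but there might be no liver value behind the entry.

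**Working it through.** There is no stated figure to reproduce. The check sets the schedule and the exit rule side by side, using Table 1 and its key, Description of Study Procedures, Compliance, Adequacy of Protection Against Risks, and Stopping rules.

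| Visit | Study drug | Safety labs | Research blood | Physical examination | Exit rule applies |
|---|---|---|---|---|---|
| Baseline 2 | starts | yes | yes | no | no |
| Week 1 | yes | no | yes | no | no |
| Week 2 | yes | no | no | no | no |
| Week 4 | yes | yes | yes | no | yes |
| Week 8 | yes | yes | yes | yes | yes |

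**Step 1: is Baseline 2 an on-drug test?** No. It is the randomization visit. The protocol does not say whether the sample comes before or after the first dose, but a sample on the day of the first dose would tell little about the drug's effect on the liver.

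**Step 2: required transaminase tests after the first dose.**
- Leaves before Week 4: 0 at Week 1 + 0 at Week 2 + 0 at exit = 0.
- Removed after the Week 4 visit and before Week 8: 1 at Week 4 + 1 at exit = 2, if the exit rule is read as covering all removals.
- Completes: 1 at Week 4 + 1 at Week 8 = 2.

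**Step 3: does another provision require a test before Week 4?**
- Reporting of gastrointestinal symptoms (Adequacy of Protection Against Risks): no test is attached.
- Recording of adverse events at Weeks 1 and 2 (Table 1): no test is attached.
- A decision about continuation after an overt study-related event (Adverse Event Reporting): no test is attached.
- Clinicians on call (Data and Safety Monitoring Plan): no test is attached.
- Removal for an allergic reaction (Stopping rules): follow-up until the reaction resolves, with no liver test named.

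Each of these can lead to a test. None of them requires one.

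**Step 4: how many women?** This cannot be derived. Section 6, Participants, gives a dropout figure of about 20 with no unit. Read as women, 120 × 50% = 60 eligible and 60 − 20 = 40, which matches the target. Read as per cent, 60 × 0.80 = 48, which does not. Neither reading says when women leave, or how many leave before the first dose (Randomization provides for those to be replaced). The number affected could be anything from none to all of the dosed dropouts.

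**Step 5: how many rises would be missed?** This cannot be derived either. The only hepatic rate in the protocol is abnormal ALT at 1% in Table 2 (414 patients). Its footnote limits that entry to values above 10 times the upper limit of normal or values that ended treatment. It is not a rate of more than two-fold rises, and it is not specific to the first four weeks.

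**The case against.** The best defence is that this is a deliberate choice that breaches nothing. The Week 4 threshold appears twice in matching terms and coincides with the first scheduled on-drug labs. No other section contradicts it. Safeguards come before and around it: liver disease is an exclusion; transaminases, hepatitis B and C and HIV are screened; safety labs are repeated at Baseline 2; alcohol is limited on drug; and the first dose is supervised. Serious reactions are managed by an unblinded physician, and adverse events go to the oversight bodies. A woman who leaves has normally stopped the drug, so the stopping rule's main action, discontinuation, has already happened.

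Most of this stands, and it is why the expected impact is low. It does not close the gap. The screening measures act before dosing, the later ones depend on symptoms or on a clinician's choice, and stopping the drug does not find or follow a silent rise.

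Three stronger readings are tempting, and the documents do not support them.
- A reader might infer that the plan fails a monitoring standard because four of the eight dosing weeks pass without a required test. The documents set no testing interval that this schedule misses. That period also applies to women who stay, whom an exit rule does not reach.
- A reader might infer, because the exit sentence follows the sentence on taking less than 75% of medication, that it covers adherence removals only. Under Stopping rules it speaks of removal without qualification, among several other criteria, so a general reading is natural. The gap exists on either reading.
- A reader might infer a count of missed liver events. That would need dropout timing and a rate of two-fold rises, and the protocol gives neither.

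**Conclusion.** The point holds as a narrow gap in participant safety. The text is clear: after the first dose, a woman who leaves before Week 4 has no required transaminase test and no required exit examination. This is a stated rule with a cut-off, not a missing detail, and the cut-off works against the protocol's own aim of following a more than two-fold rise to baseline.

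The size is low and cannot be put as a number. The conclusion about the text needs no numerical assumption. The judgement that the impact is low rests on two: that an early leaver has normally stopped the drug, and that clinicians would order a test for some of the women with symptoms. The glutamate result is not affected. This is a cheap improvement worth considering, not a fault that puts the trial in doubt.

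**What to change.** Under Compliance (Section 6) and Stopping rules (Section 12), replace the Week 4 condition with a general rule, for example: *Every woman who has taken at least one dose of study medication and is removed or withdraws, at any time and for any reason, will be asked to have the exit safety panel, including ALT and AST, and the physical examination.*

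Set it apart from the adherence sentence so that its scope is plain. Naming withdrawal as well as removal covers women who leave by their own choice. Naming ALT and AST ties the exit panel to the transaminase rule. She is asked, because a woman who withdraws may decline.

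The cost is a wording change in two places plus one routine panel and one examination per early leaver, using procedures the trial already has. The total cannot be stated because the timing of dropouts is not given. The visit schedule for women who stay is unchanged.

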#### Composition of the Data Safety Monitoring Board (DSMB)

Frequency of DSMB review for this protocol will follow recommendations from the IRB based on the assessed risk status of the study. The DSMB for this study will consist of the Clinical Research Oversight Committee with members including [name]. Chairman, [name] M.D., [name] and [name] MA. They have agreed to serve as the external DSMB for investigator initiated clinical trials conducted by Emory researchers in the Department of Psychiatry & Behavioral Sciences. If the DSMB requires additional specialized expertise to evaluate safety issues related to the performance of this study, a relevant specialist will be consulted by the DSMB.

#### Procedures and Responsibilities of the DSMB

The DSMB will meet monthly. This protocol will be submitted to the DSMB simultaneously with the initial submission to the Emory IRB. The DSMB will review the research protocol and plans for data and safety monitoring. Once per year (or after 6 months if the protocol is considered 'high risk' by the IRB), the DSMB will review a report from the study's data manager that includes: the number of participants who signed consent for the study and were randomized, the number of post-randomization dropouts, reasons for these dropouts, and any safety concerns, adverse events, an up-to-date consent form, and measures taken to protect confidentiality (e.g., data and tape storage, use of coded ID numbers, etc.). The DSMB will also review the Principal Investigator's summary of any new data or evidence that might alter the risk/benefit ratio for participating in the study (e.g., newly published studies, etc.). After reviewing this information, the DSMB will issue its own report summarizing any serious and unexpected adverse events or other unanticipated problems that involve risk to study participants, and whether these appear related to the study-based interventions or research assessment protocols.

There will be regular, ongoing communication between the PI, Emory's IRB, and the DSMB. The PI will take responsibility for submitting reportable serious and unexpected adverse events or other unanticipated study problems to Emory's IRB according to standard regulations. A copy will be sent to the DSMB. Actions taken by the IRB in response to adverse event reports will be immediately reported to the DSMB.

